8.1 Screening

Molecular pre-screening

Not Applicable

Screening

Patients diagnosed with either aGvHD (grades II-IV) or SR-aGvHD (grades II-IV) after alloSCT will be consented to the study prior to any study procedures being performed.

Screening period will begin once the patient has signed the Study Informed Consent and will be a maximum of 28 days (Day -28 to Day -1).

Screening procedures are outlined in the visit evaluation schedule ([Table 8-1](#)) including blood samples tested as needed, and assessment of inclusion and exclusion criteria.

All study procedures should be performed within 28 days before treatment initiation on Day 1. Laboratory assessments should be performed within 72 hours of treatment initiation. Continued use of systemic corticosteroids, CNI (cyclosporine or tacrolimus), and topical corticosteroid therapy per institutional guidelines is permitted. Other systemic medications for aGvHD may be continued after Day 1 only if used for aGvHD prophylaxis prior to diagnosis of aGvHD. For SR-aGvHD patients, cessation of other systemic treatment for aGvHD other than corticosteroids +/- CNI will be required prior to treatment initiation.

A patient who has a laboratory test result(s) that does not satisfy the entrance criteria may have the test(s) repeated. These tests may be repeated as soon as the investigator believes the retest result is likely to be within the acceptable range to satisfy the entrance criteria, and can be completed within the 28 day screening period. In this case, the patient will not be required to sign another ICF, and the original patient ID number assigned by the investigator will be used.

All baseline assessments should be performed on Day 1 as per [Table 8-1](#). Laboratory assessments performed within 72 hours of Day 1 need not be repeated.

A patient is considered a screen failure in the event that the laboratory test(s) cannot be available within the screening period, or the retest(s) do not meet the entrance criteria or the patient's medical condition has changed significantly during the screening period so that the inclusion/exclusion criteria are no longer met, more details outlined on [Section 5](#).

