8.2 Subject demographics/other baseline characteristics

Patient information to be collected at screening include:

- a. Demography
- b. Complete Medical History and current medical conditions
- c. Prior and concomitant medications and non-therapies (including physical therapy, oxygen and blood transfusions)
- d. Disease History – disease treatment history, donor background, stem cell transplant and GvHD disease history including CIBMTR classification ([Section 16.5](#) Appendix 5) and HCT specific comorbidity index score ([Section 16.4](#) Appendix 4)

Patient will have the screening assessments performed before the start of study treatment as in [Table 8-1](#):

- Physical examination including height, weight, vital signs
- Laboratory assessments – Hematology, Chemistry, Coagulation, Urinalysis
- Hepatitis serology markers
- Pregnancy test (for applicable female patients only, [Section 8.5.5](#))
- Graft failure assessment

- aGvHD disease staging ([Table 8-2](#)) ([Harris et al 2016](#)) Biopsy confirmation of aGvHD is recommended but is not required. Enrollment should not be delayed awaiting biopsy or pathology results.
- Graft failure baseline assessment

■

The investigator must confirm all the inclusion and exclusion criteria prior to contacting IRT for dose assignment. Once the patient's eligibility is confirmed, the patient must have baseline assessments performed on Day 1 prior to treatment initiation ([Table 8-1](#)).

Please refer to sections below for related assessments.

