3.1.1 General definitions

Investigational drug and study treatment

Investigational drug/study treatment, will refer to the ruxolitinib in this single arm study.

Date of first administration of study treatment

The date of first administration of study treatment is derived as the first date when a nonzero dose of study treatment was administered as per the DAR eCRF. The date of first administration of study treatment will also be referred as *start of investigational drug*.

Date of last administration of study treatment

The date of last administration of study treatment is defined as the last date when a nonzero dose of study treatment was administered as per DAR eCRF. The date of last administration of study treatment will also be referred as *end of investigational drug*.

Study day

The study day, describes the day of the event or assessment date, relative to the reference start date.

The study day is defined as:

- The date of the event (visit date, onset date of an event, assessment date etc.) – reference start date + 1 if event is on or after the reference start date;
- The date of the event (visit date, onset date of an event, assessment date etc.) – reference start date if event precedes the reference start date.

The reference start date for all assessments (e.g. safety, efficacy, PK, [REDACTED], etc.) is the start of study treatment.

The study day will be displayed in the data listings. If an event starts before the reference start date, the study day displayed on the listing will be negative.

Time unit

A year length is defined as 365.25 days. A month length is 30.4375 days (365.25/12). If duration is reported in months, duration in days will be divided by 30.4375. If duration is reported in years, duration in days will be divided by 365.25.

Baseline

For safety and efficacy evaluations, the last available assessment on or before the date of start of study treatment is defined as “baseline” assessment.

If patients have no value as defined above, the baseline result will be missing.

On-treatment assessment/event and observation periods

The overall observation period will be divided into three mutually exclusive segments:

1. ***pre-treatment period***: from day of patient’s informed consent to the day before first administration of ruxolitinib
2. ***on-treatment period***: from date of first administration of study treatment to 30 days after date of last actual administration of ruxolitinib (including start and stop date)

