3.8 Safety analyses

For all safety analyses, the safety set will be used. All listings and tables will be presented by group. If the Phase I starting dose is different to RP2D, the safety data will be listed and summarized by age group and dose level. For safety evaluations (except for AE), the last available assessment on or before the date of start of study treatment is taken as the “baseline” assessment.

Safety summaries (tables, figures) include only data from the on-treatment period with the exception of baseline data which will also be summarized where appropriate (e.g. change from baseline summaries). In addition, a separate summary for death including on treatment and post treatment deaths will be provided. In particular, summary tables for (AEs) will summarize only on-treatment events, with a start date during the on-treatment period (*treatment-emergent* AEs).

The on-treatment period lasts from the date of first administration of ruxolitinib to 30 days after the date of the last actual administration of ruxolitinib.

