3.8.3 Laboratory data

Laboratory, data from all sources (central and local laboratories) will be combined.

Grading of laboratory values will be assigned programmatically as per NCI Common Terminology Criteria for Adverse Events (CTCAE) version 4.03. The calculation of CTCAE grades will be based on the observed laboratory values only, clinical assessments will not be taken into account.

CTCAE Grade 0 will be assigned for all non-missing values not graded as 1 or higher.

For laboratory tests where grades are not defined by CTCAE v4.03, results will be categorized as low/normal/high based on laboratory normal ranges.

The following summaries will be produced for hematology and biochemistry laboratory data (by laboratory parameter and group):

- Shift tables using CTC grades to compare baseline to the worst on-treatment value
- For laboratory tests where CTC grades are not defined, shift tables using the low/normal/high/(low and high) classification to compare baseline to the worst on-treatment value.

The following listings will be produced for the laboratory data:

- Listings of all laboratory data, with CTC grades and classification relative to the laboratory normal range. Lab data collected during the post-treatment period will be flagged.
- Listing of all CTC grade 3 or 4 laboratory toxicities

The results from viral load testing will be listed.

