² Fleming S, Thompson M, Stevens R, et al. Normal ranges of heart rate and respiratory rate in children from birth to 18 years of age: a systematic review of observational studies. Lancet 2011; published online March 15. DOI:10.1016/S0140-6736(10)62226-X.

³ Gender percentiles categories (P3, P5, P10, P25, P50, P75, P85, P90, P95, P97) are obtained from the CDC Growth Charts

The number and percentage of patients with notable vital sign values (high/low) will be presented.

A listing of all vital sign assessments will be produced and notable values will be flagged. In the listing, the assessments collected outside of on-treatment period will be flagged.

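### A Day 1 pre-dose record counts as both baseline and on-treatment, so for those patients the shift tables cannot show improvement and notable vital sign counts include pre-dose values

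*SAP*

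**What the plan says.** Four rules meet on Study Day 1.

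- **Baseline.** SAP 3.8 says that for safety evaluations other than adverse events, "the last available assessment on or before the date of start of study treatment is taken as the" baseline. SAP 3.1.1 gives the same rule for safety and efficacy.
- **Periods.** SAP 3.1.1 divides observation into three segments that may not overlap. Pre-treatment runs from "informed consent to the day before first administration of ruxolitinib". On-treatment runs "from date of first administration of study treatment to 30 days after date of last actual administration of ruxolitinib (including start and stop date"). SAP 3.8 repeats the start: "The on-treatment period lasts from the date of first administration of ruxolitinib".
- **Timing of assessments.** Protocol 8.2 says "the patient must have baseline assessments performed on Day 1 prior to treatment initiation", and Table 8-1 schedules vital signs, hematology and chemistry on Day 1. Protocol 8.1 makes one exception: "Laboratory assessments performed within 72 hours of Day 1 need not be repeated".
- **Outputs.** SAP 3.8.3 specifies "Shift tables using CTC grades to compare baseline to the worst on-treatment value", with low/normal/high tables for tests that have no grades. SAP 3.8.4.2 summarizes vital signs collected on treatment and adds: "The number and percentage of patients with notable vital sign values (high/low) will be presented". Neither section limits these outputs to values after baseline or after the first dose.

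**The concern.** Applied as written, the date rules place one pre-dose record on both sides of a before-and-after comparison. Abnormal values at entry are to be expected here. Protocol 5.1 admits platelet counts just above 20,000/µl, a range that Table 6-3 labels Grade 4, and Protocol 4.5 says that raised liver tests cannot be used to exclude patients. With no control arm, a reader has no comparator against which to judge the on-treatment totals. The handling also depends on something unrelated to the drug: a sample drawn on Day -1 is pre-treatment, so later improvement can show, while the same result drawn on Day 1 is on-treatment, so it cannot.

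**Working it through.** The documents state no figure for this point, so there is none to reproduce. The check applies the date rules record by record and then counts the consequences.

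**1. Where each record falls** (SAP 3.1.1)

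| Study day | Eligible as baseline | Period |
|---|---|---|
| -3, -1 | yes | pre-treatment |
| 1 | yes | on-treatment |
| 2, 7 | no | on-treatment |

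Only Day 1 is both. The rules use dates, not clock times, so a pre-dose Day 1 value cannot be classed as pre-treatment.

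**2. Who is affected**

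- *Vital signs:* children assessed on Day 1 as scheduled. The waiver in Protocol 8.1 covers laboratory tests only.
- *Laboratory tests:* only children whose baseline sample was drawn on Day 1. A sample carried over from the preceding 72 hours is pre-treatment and does not overlap. The documents do not say how many children fall in each group.

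**3. Shift tables**

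Grades 0 to 4 give 5 × 5 = 25 cells. With a Day 1 baseline of grade b and a worst post-dose grade w, the table reports max(b, w), which cannot be below b.

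- Cells that can be filled: 5 + 4 + 3 + 2 + 1 = 15.
- Cells that cannot: 25 − 15 = 10, and all of them are improvements.
- Cells turned into a false worsening by a single baseline record: 0, because max(b, w) exceeds b only when w does.

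Example: a child with platelets of 22,000 before dosing on Day 1 is Grade 4 at baseline and Grade 4 at worst on treatment, whatever the later counts. Two edge cases follow. A child with no post-dose sample still receives an on-treatment value. A child with two Day 1 records could show a worsening if the earlier pre-dose value was the worse one.

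**4. Notable vital signs**

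The limits for blood pressure, pulse and temperature in SAP Table 3-4 are absolute, so a pre-dose Day 1 value can meet them. Weight and height are judged as change from baseline, so the baseline record cannot be notable and those counts are unaffected.

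Let p0 be the share of children notable on Day 1 before dosing, and q the share of those who are notable again at least once after dosing. Only those not notable again are counted wrongly:

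excess = 45 × p0 × (1 − q)

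The 45 is the completed enrollment in the Amendment 3 rationale. The documents give neither p0 nor q; the values below are assumptions.

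| p0 | q = 30% | q = 50% | q = 80% |
|---|---|---|---|
| 5% | 1.57 | 1.12 | 0.45 |
| 10% | 3.15 | 2.25 | 0.90 |
| 20% | 6.30 | 4.50 | 1.80 |
| 30% | 9.45 | 6.75 | 2.70 |

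The ends of the range are 45 × 0.05 × 0.20 = 0.45 and 45 × 0.30 × 0.70 = 9.45.

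**The case against.** The best defence is that the SAP treats baseline as a category of its own. Sections 3.1.1 and 3.8 allow baseline data to be summarized as an exception to the on-treatment rule, and the visit-window table maps everything up to Study Day 1 to baseline. Comparing baseline with the worst on-treatment value most naturally means two different records, and programmers may drop the baseline record by convention.

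That reading is sensible, but the text does not state it. The exception lets baseline be shown as well; it does not take a Day 1 baseline out of the on-treatment period. The windows govern by-visit summaries, not worst-ever values or any-time counts, and that table lists its Day 1 baseline row under an on-treatment heading.

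Other parts of the defence stand. The shift table displays the baseline grade, so a child already Grade 4 is visibly so. A worst-value table is a poor display of recovery in any case: even after the change, a child must be better at every later on-treatment assessment to appear improved. SAP 3.8.1 counts only new or worsening adverse events, and full listings of laboratory and vital sign data are planned. Protocol 5.2 excludes uncontrolled hypertension, which should lower p0 for blood pressure.

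Two stronger inferences should be resisted. A reader might conclude that the shift tables present pre-drug abnormality as drug-induced worsening; a single Day 1 record lies on the diagonal and does not. A reader might also take the number of children abnormal on Day 1 as the size of the error. That is a baseline count: children abnormal again after dosing belong in the on-treatment count under any rule, and laboratory samples carried over from before Day 1 do not overlap at all. Similarly, the chance of at least one high reading over many visits is a matter of repeated measurement and does not measure this overlap.

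**Conclusion.** The point holds in a limited form. For patients with a Day 1 baseline, the written rules hide improvement in the shift tables and inflate worst-grade column totals; in the notable counts for blood pressure, pulse and temperature they include children who were notable only before ruxolitinib. The structural result (10 of 25 cells unreachable) follows from the definitions alone. The vital sign excess of about 0.5 to 9.5 of 45 children rests entirely on the assumed p0 and q. The laboratory effect cannot be sized in patients, because the share with a Day 1 sample is not given. The ORR analyses at Days 28 and 56 do not use these tables. It is still worth correcting, because the stated rule yields a wrong count rather than merely lacking detail.

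**What to change.** Leave the on-treatment period as defined. Add to SAP 3.8.3 and 3.8.4.2 a sentence to this effect: *worst on-treatment and notable-value summaries use only records after the baseline record, that is, from Study Day 2 onward.* Because the cut is by date, no clock times of dosing or assessment are needed. It also removes the case of several Day 1 records. In the notable vital sign table, show separately the children already notable at baseline and those newly notable.

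The cost is one sentence, a post-baseline flag in the analysis datasets and a split in one table; no new data are required. There is a small downside: a true post-dose value on Day 1, if any exists, would not be counted.

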3.8.4 Other safety data

3.8.4.1 ECG and cardiac imaging data

Not applicable

3.8.4.2 Vital signs

Vital sign assessments are performed in order to characterize basic body function. The following parameters were collected: height or body length (cm), weight (kg), body temperature (°C), pulse (beats per minute), systolic and diastolic blood pressure (mmHg). The body surface area (BSA in m²) and body mass index (BMI in kg/m²) are derived using the following formulas:

BSA: (Height (cm) x Weight(kg) / 3600) ^ 0.5

BMI: Weight(kg) / Height² (m²)

Data handling

Vital signs collected on treatment will be summarized. Values measured outside of on treatment period will be flagged in the listings.

Clinically notable vital sign criteria for blood pressure or weight (see below) are based on the height/body length of the subject. Since height/body length might not be measured at each visit, the last available height/body length value before that assessment date will be used instead, i.e. using LOCF as imputation method.

Data analysis

For analysis of vital signs the clinically notable vital sign criteria are provided in [Table 2-4](#) below.

Table 3-4 Clinically notable changes in vital signs

Vital Sign	High	Low
Systolic blood pressure [mmHg]	≥ 95th percentile of the age and height group ¹	≤ 5th percentile of the age and height group ¹
Diastolic blood pressure [mmHg]	≥ 95th percentile of the age and height group ¹	≤ 5th percentile of the age and height group ¹
Body temperature [°C]	≥ 38.4°C	≤ 35.0°C
Pulse rate [bpm] ²	12-≤18 months > 140 18-≤24 months > 135 2-≤3 years > 128 3-≤4 years > 123 4-≤6 years > 117 6-≤8 years > 111 8-≤12 years > 103 12-≤15 years > 96 ≥ 15 years > 92	12-≤18 months < 103 18-≤24 months < 98 2-≤3 years < 92 3-≤4 years < 86 4-≤6 years < 81 6-≤8 years < 74 8-≤12 years < 67 12-≤15 years < 62 ≥ 15 years < 58
Weight	increase from baseline ³ of ≥ 2 BMI-for-age percentile categories ³	decrease from baseline ³ of ≥ 2 BMI-for-age percentile categories ³
Height	increase from baseline of ≥ 2 height-for-age/gender percentile categories ³	decrease from baseline of ≥ 2 height-for-age/gender percentile categories ³

bpm=beats per minute; CDC= Centers for Disease Controls and prevention;

¹ Blood pressure percentiles are calculated for each blood BP record using the method described in Appendix B of the following reference: The Fourth Report on Diagnosis, Evaluation and Treatment of High Blood Pressure in Children and Adolescents. Pediatrics 2004; 114; 555.

² Fleming S, Thompson M, Stevens R, et al. Normal ranges of heart rate and respiratory rate in children from birth to 18 years of age: a systematic review of observational studies. Lancet 2011; published online March 15. DOI:10.1016/S0140-6736(10)62226-X.

³ Gender percentiles categories (P3, P5, P10, P25, P50, P75, P85, P90, P95, P97) are obtained from the CDC Growth Charts

The number and percentage of patients with notable vital sign values (high/low) will be presented.

A listing of all vital sign assessments will be produced and notable values will be flagged. In the listing, the assessments collected outside of on-treatment period will be flagged.

3.8.4.3 Cumulative incidence of grade 3 infection

Cumulative incidence curves for time to grade ≥ 3 infections as well as estimates at 1, 2, 6 months etc. with 95% confidence intervals will be presented overall and for each age group (if sufficient number of patients are available in the age groups) as well as by treatment-naïve vs SR-cGvHD, considering death or discontinuation from study treatment (due to any reason) without prior infection as competing risks.

3.8.4.4 Acceptability and Palatability assessment

All acceptability and palatability assessment data will be summarised and listed by age group and formulation.

3.9 Pharmacokinetic endpoints

Pharmacokinetic Analysis Set (PAS) will be used in all pharmacokinetic data analysis and PK summary statistics.

In patients with extensive PK sampling on Day 1 (samples 1 to 8 described in [Section 8.6.1.1 of the protocol](#)), PK parameters of ruxolitinib will be calculated by non-compartmental methods using Phoenix WinNonlin (Pharsight, Mountain View, CA) software. The following parameters will be calculated ([Table 2-5](#)). Additional PK parameters may be estimated as needed.

Table 3-5 Non-compartmental pharmacokinetic parameters of ruxolitinib

AUClast	The AUC from time zero to the last measurable concentration sampling time (Tlast)
AUCinf	The AUC from time zero extrapolated to infinity
AUC0-12	The AUC from time zero extrapolated to 12 hours
Cmax	The maximum (peak) observed plasma drug concentration
Ctrough	The minimum observed plasma concentration at the end of an administration interval (corresponding to the pre-dose concentration prior to the following administration)
Tmax	The time to reach maximum (peak) plasma, blood, serum, or other body fluid drug concentration after single dose administration (time)
T1/2	The elimination half-life associated with the terminal slope (Lambda_z) of a semi logarithmic concentration-time curve
CL/F	The total body clearance of drug from the plasma
Vz/F	The apparent volume of distribution during terminal phase (associated with Lambda_z)

All plasma concentrations will be analyzed using a population PK approach.

Statistical methods for pharmacokinetic analyses

All individual plasma ruxolitinib concentrations data will be listed by group. Descriptive summary statistics will be provided by group at each scheduled time point. Summary statistics will include n (number of patients with non-missing values), mean (arithmetic and geometric), SD, CV (arithmetic and geometric), median, minimum and maximum. Individual profiles with median by dose level as well as arithmetic mean with SD and geometric mean ruxolitinib plasma concentration versus time profiles by treatment will be displayed graphically.

Ruxolitinib plasma PK parameters data will be listed by group. Descriptive statistics (n, arithmetic mean, standard deviation (SD), coefficient of variation (CV)% for mean, geometric mean, geometric CV%, median, minimum and maximum) will be provided for all PK parameters by dose level except for Tmax where median, minimum and maximum will be presented.

If the Phase I starting dose is different to RP2D, PK data will be listed and summarized by age group and dose level.

Population PK approach on pooled Phase I and Phase II data

Nonlinear mixed effects modeling (population PK) or other model-based approaches, as appropriate, will be used to analyse the concentration data from all patients. Details of the analysis methods will be developed in a PK analysis plan and the population PK analysis will be documented in a separate report.

During modeling of the pharmacokinetics of study treatment, the broad principles outlined in the FDA guidance will be followed (*Guidance for Industry: Population Pharmacokinetics*; <http://www.fda.gov/cder/guidance/1852fnl.pdf>).

Data handling principles

All concentration values below the lower limit of quantitation (LLOQ) are set to zero by the Bioanalyst, and will be displayed in the listings as zero and flagged. LLOQ values will be treated as zero in any calculations of summary statistics, and treated as missing for the calculation of the geometric means and their CV%. The number of non-zero concentrations will also be reported in the summary statistics.

Missing values for any PK data will not be imputed and will be treated as missing.

